3.3 Study Endpoints

Pilot Study

- Comparison of taste tests before and during chemotherapy

RCT

Primary endpoint:

- Comparison of the perception of bitterness induced by 500 ppm caffeine from week 1 to week 3 between the study group (HED mouthwash) and the control group (water mouthwash).

Secondary endpoints:

- Comparison of the perception of bitterness triggered by 500 ppm caffeine from week 1 to week 12 between the two groups.
- Comparison of the threshold for bitterness perception from week 1 to week 3 between the two groups.
- Comparison of the threshold for bitter taste perception in week 3 between the two groups.
- Comparison of overall taste perception in week 3 between the two groups.
- Comparison of overall taste perception from week 1 to week 12 between the two groups.
- Comparison of food intake using a 24-hour recall from week 1 to week 12 within the two groups.
- Comparison of food intake using a 24-hour recall from week 1 to week 12 between the two groups.
- Comparison of improvements in body composition from week 1 to week 12 between the two groups.

- Comparison of weight gain from week 1 to week 12 between the two groups.
- Comparison of quality of life using the EORTC-QLQ-30 Ovar and OV-28 from week 1 to week 12 within the two groups.
- Comparison of the change in quality of life using the EORTC-QLQ-30 Ovar and OV-28 from week 1 to week 12 between the two groups.
- Comparison of “patient-related outcomes” using a diary from week 1 to week 12 within the two groups.

4. Experimental Protocol

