The patient returns for screening one week after her last cycle of chemotherapy due to suspected bitter phantogeusia. The patient's bitter phantogeusia is determined by directly asking about bitter taste perception ("Did you notice an increased bitter taste during the course of chemotherapy?") and subsequently classifying the increased perception as "mild," "moderate," or "severe." If the patient rates her heightened perception of bitterness as "moderate" or "severe," meets all inclusion and exclusion criteria, and consents to the study by signing the patient information form, she is eligible for inclusion in the study. As part of the screening examination, the threshold for bitter perception and the bitter perception triggered by 500 ppm caffeine are recorded. Body composition is also measured using the BOD POD® and a weight check is performed. Quality of life is assessed using the EORTC-QLQ-30 Ovar and OV-28, and dietary intake is assessed using a 24-hour recall questionnaire (GloboDiet). In addition, perception of the other four basic tastes (sweet, sour, salty, umami) is determined using a sensory test. Furthermore, the patient is given a detailed explanation of the necessary follow-up visits required as part of the study and is handed a diary.

Visit 2

The patient returns for a follow-up visit three weeks after the end of her last course of chemotherapy. A test is conducted to assess bitterness perception of 500 ppm caffeine and to determine the bitterness perception threshold, as well as a sensory test to assess perception of the taste qualities sweet, sour, salty, and umami, a quality-of-life assessment using the EORTC-QLQ-30 Ovar and OV-28, and a dietary intake assessment using the 24-hour recall questionnaire (GloboDiet).

Visit 3

The patient returns 12 weeks after the end of her last chemotherapy session for a final examination. A test of bitterness perception using 500 ppm caffeine and determination of the bitterness perception threshold is performed, along with a sensory test to assess perception of the taste qualities sweet, sour, salty, and umami, a measurement of body composition using the BOD POD®, and a weight check. Quality of life is assessed using the EORTC-QLQ-30 Ovar and OV-28, and dietary intake is assessed using a 24-hour recall questionnaire (GloboDiet). The diary is discussed and collected.

RCT: Overview of Study Visits

	CRF	QoL (EORTC 30 and OV-28)	Medication dispense/return	Sensory test	BOP POD	Weight	Diary	24-hour recall

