4.3. Study Medication

4.3.1. Production and Storage:

To prepare the study medication, 30 mg of homoeriodictyol sodium is granulated with food coloring, a opacifier, and a carrier material (manufactured by Symrise AG, Holzminden, Germany) and packaged in airtight bags. The powder are portioned and packed into the bags at the Institute of Physiological Chemistry using portioning spoons. The number of bags containing the portioned powder required for each study participant is collected in cardboard boxes, which are labelled for each patient according to the randomization (sequential numbers from 1 to 32). This labelling is performed by a staff member of the Institute of Physiological Chemistry who will have no contact with the study participants. The process is carried out in accordance with internationally established standards and standard operating procedures (SOPs).

The study medication is stored in the cold room (4–6°C) of the Institute of Physiological Chemistry until it is dispensed. For this purpose, the boxes labelled according to randomization are kept in a sealed aluminium box. After the study medication is dispensed to the patient, the cardboard box containing the entire medication is stored in the patient's refrigerator.

The study participants dissolve the powder in 20 ml of water immediately before use. The placebo consists of the same formulation of powder, except that the HED is replaced by a carrier substance, which the study participants also dissolve in 20 ml of water.

4.3.2. Blinding:

The study medication, both the verum and the placebo, is packaged in cardboard boxes and labelled according to randomisation.

4.3.3. Randomisation:

Randomisation is done online using the randomisation programme of the Medical University of Vienna (<https://www.meduniwien.ac.at/randomizer/web/login.php>). Patients are randomised in a 1:1 ratio without further stratification and without blocks. Randomisation of the patient takes place after the informed consent has been signed, the inclusion and exclusion criteria have been checked, the taste test has been carried out, and the impaired bitter perception has been objectively assessed (recording of the threshold for bitter perception and the bitter perception triggered by 500 ppm caffeine). If impaired bitter perception cannot be verified, the patient is documented as a 'screening failure' and excluded from the study. For further details, see 'Statistical section: Randomisation'.

4.3.4. Dosage:

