4.5. Timeline

Pilot study

Recruitment	Months 1–12
Analysis	Months 12–15
Total	15 months

RCT

Study planning	Months 1–6
Recruitment	Months 7–30
Analysis	Months 30–36
Total	36 months

B) Statistical Section

1. Sample Size

Forty patients will be recruited for the pilot study. This study is intended to provide a descriptive analysis of taste changes during chemotherapy and to validate the tests used for the double-blind, randomized, placebo-controlled study planned afterwards. The double-blind, randomized, placebo-controlled study will include 32 female patients. Based on current studies [3], the prevalence of bitter phantogeusia is approximately 30–78%. An HED mouthwash leads to a 30% reduction in bitter perception (standard deviation 10%) [7], which describes the expected effect size. The primary endpoint is defined as “comparison of the bitter perception triggered by 500 ppm caffeine from week 1 to week 3 between the study group (HED mouthwash) and the control group (water mouthwash).” The patient rates bitterness perception on a continuous scale from 0 to 10. The study endpoint is therefore a continuous variable. The data from week 1 and week 3 will be analysed using a paired t-test to compare the intervention group with the control group. Taking into account a 20% dropout rate, a 90% power level, and a significance level of 1%, this results in a sample size of 32 patients. These will be randomized 1:1, resulting in a group size of 16 patients each. Approximately 77% of patients experience bitter phantosmia following platinum-based combination chemotherapy. Therefore, approximately 40 patients will need to be screened.

2. Randomization

Randomization is performed online using the randomization program of the Medical University of Vienna (<https://www.meduniwien.ac.at/randomizer/web/login.php>). The complete randomization list is provided to [name], MSc, a staff member of the Institute of Physiological Chemistry. Study medication is packaged and coded, with coding performed exclusively by [name]. The coded, randomized study medication is then distributed as needed to the investigators, who administer the study medication to the patients. The investigators and the statistician may not view the randomization list until the study has been completed.

3. Statistical Analysis

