The efficacy of the treatment is defined as a reduction in the perception of bitterness by more than 30% in the treatment group compared to the placebo group. The primary endpoint will be evaluated using a paired t-test.

This will be evaluated in two analyses:

- Intention-to-treat analysis: Inclusion of all patients who used the mouthwash at least once
- Per-protocol analysis: Inclusion of patients who completed the study according to the study protocol

Secondary endpoints are also analysed using intention-to-treat and per-protocol analyses. The collected clinical and pathological data are presented descriptively using absolute values or, depending on the normality of the distribution, using the median (interquartile range) or mean (standard deviation). Metric variables are compared using Student's t-test or the Mann-Whitney U test, depending on normal distribution. Categorical variables are compared using the chi-square test and, if feasible given the number of groups, presented including the odds ratio (95% confidence interval). The study will investigate predictive factors for response to the intervention. These analyses are performed using a multivariate binary logistic regression model. The following variables are included: patient age, number of chemotherapy cycles, patient BMI, bowel resection during the primary surgery, peripheral polyneuropathy during chemotherapy, nausea at the time of study enrolment, and diarrhoea at the time of study enrolment. Version 21.0 of the statistical software SPSS (SPSS, Inc.) is used for the statistical analysis.

Patient data is pseudonymized, documented, and analysed in accordance with current data protection regulations and is not disclosed to third parties. The data is published in anonymized and aggregated form.

C) Ethical and Legal Section

1. Ethical Aspects

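### The caffeine rating taken before randomisation is not a covariate in any planned between-arm analysis; adjusting for it costs almost nothing and usually gives a more precise estimate

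*Combined protocol and SAP*

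**What the plan says.** At RCT Visit 1 (section 4.1.1), "the threshold for bitter perception and the bitter perception triggered by 500 ppm caffeine are recorded". Section 4.3.3 places randomisation after the taste test and the objective bitter assessment, and treats patients without verified impairment as screening failures. Every randomised patient therefore has a caffeine rating that predates allocation. Visit 2, two weeks later, repeats it. The Sample Size section treats the 0 to 10 rating as continuous.

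On allocation, section 4.3.3 says: "Patients are randomised in a 1:1 ratio without further stratification and without blocks".

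On analysis, the Statistical Analysis section says "The primary endpoint will be evaluated using a paired t-test", as does the Sample Size section in other words. For other outcomes it says: "Metric variables are compared using Student's t-test or the Mann-Whitney U test, depending on normal distribution". The only regression is a logistic model for predictors of response. It lists seven variables, and the week-1 rating is not one of them.

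Several secondary endpoints in section 3.3 are also between-arm comparisons with a Visit 1 value, for example "Comparison of food intake using a 24-hour recall from week 1 to week 12 between the two groups".

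**The concern.** A paired t-test compares visits within patients, not arms, so that sentence has to be rewritten in any case. The obvious replacement is a two-sample t-test on the week 1 to week 3 change. That would cure the pairing problem but would still not make the best use of the baseline.

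A change score fixes the slope of week 3 on week 1 at 1. A single 0 to 10 rating repeated after two weeks will normally have a slope below 1, so the arm that happens to start higher will tend to fall further through regression to the mean. With about 13 evaluable patients per arm and no stratification on the rating, a noticeable baseline difference is not rare. Two things are at stake: the precision of the primary comparison, and how far its estimate depends on the baseline difference that the randomisation happens to produce. The estimate matters beyond the p-value, because the risk-benefit section says the data are to help plan a larger validation study.

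**Working it through.** **Inputs from the Sample Size section.** 32 patients, 16 per arm; 20% dropout, so 32 × 0.8 = 25.6, about 26 evaluable or 13 per arm; 90% power; 1% level with sidedness not stated (two-sided used here); 30% reduction with SD 10%.

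**Not in the documents, so assumed.** The week 1 to week 3 correlation ρ (range 0.3 to 0.95 shown) and the SD of the rating at each week (taken as equal, σ, until step 4).

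**1. The plan's own figure.** The standardised effect is 30/10 = 3.0. The exact two-sided t calculation needs 6 per arm, and 12/0.8 = 15 in total, not 32. The stated size does not follow from its inputs. That is a separate matter and nothing below depends on it. At 13 per arm, a two-sample t-test has 90% power for an effect of 1.63 SDs of the change, about half of 3.0.

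**2. Chance imbalance.** With equal SDs, a baseline difference D between arms shifts the change-score estimate by −(1−ρ)D.
- The SD of D at 13 per arm is √(2/13) = 0.392σ.
- At ρ = 0.5, an imbalance of one such SD shifts the estimate by 0.5 × 0.392σ = 0.196σ, about 0.20σ.
- The chance that D exceeds 0.5σ in either direction is about 20% at 13 per arm and 16% at 16 per arm.
- A D of 0.5σ shifts the estimate by 0.35σ at ρ = 0.3, 0.25σ at ρ = 0.5 and 0.15σ at ρ = 0.7. In simulation the shift under ANCOVA was about 0.01σ or less.

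**3. Precision and power.** The change-score variance is proportional to 2(1−ρ)σ² and the ANCOVA variance to (1−ρ²)σ², so their ratio is (1+ρ)/2. Estimating the slope from 26 patients multiplies the ANCOVA variance by about 1 + 1/22 = 23/22. Power was simulated with 40,000 trials per ρ at 13 per arm and two-sided 1%, with the effect set so that the change-score t-test has 90% power.

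| ρ | (1+ρ)/2 | × 23/22 | Simulated variance ratio | ANCOVA power (change score 90%) |
|---|---|---|---|---|
| 0.3 | 0.650 | 0.680 | 0.68 | about 98% |
| 0.5 | 0.750 | 0.784 | 0.79 | about 96% |
| 0.7 | 0.850 | 0.889 | 0.89 | about 93% |
| 0.8 | 0.900 | 0.941 | 0.95 | about 92% |
| 0.9 | 0.950 | 0.993 | 0.99 | about 90% |
| 0.95 | 0.975 | 1.019 | 1.02 | about 89% |

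The break-even for variance is (1+ρ)/2 × 23/22 = 1, so ρ = 44/23 − 1 = 0.91.

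**4. Unequal SDs.** If the week-3 SD is k times the week-1 SD, the ratio before the slope cost is k²(1−ρ²)/(1 + k² − 2ρk). With k = 1.3:
- ρ = 0.5: 1.2675/1.39 = 0.91, and × 23/22 = 0.95.
- ρ = 0.7: 0.8619/0.87 = 0.99, and × 23/22 = 1.04.

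The gain is small in the first case and slightly negative in the second. A smaller week-3 SD can move the ratio the other way.

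**5. The plan's literal effect.** At a standardised effect of 3.0 and 13 per arm, both analyses had simulated power of at least 99.8% for every ρ tried.

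**6. Type I error.** With no treatment effect, the change-score t-test rejected in 0.9% to 1.1% of simulated trials at nominal 1%, and ANCOVA did the same.

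**The case against.** The strongest reply is that an unadjusted between-arm comparison of changes is a legitimate analysis. Randomisation balances the baseline in expectation, the estimate is unbiased over repeated randomisations, and the type I error holds. All of this stands. A reader might infer that leaving out the covariate makes the primary result invalid, or that unstratified allocation does nothing for baseline balance. The documents support neither. What shifts is the estimate given the imbalance actually observed.

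A reader might also infer that the primary test is bound to lose power. That does not follow either. On the plan's own effect and SD there is no power to gain. The gains in the table need a true effect of about 1.63 SDs of the change, a ρ below about 0.9 and similar SDs at the two visits, and the documents settle none of these.

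Third, the plan names a paired test, so this point concerns a replacement that is not yet written. That is fair: the paired test is the larger defect, and this point bears on how to repair it. It remains distinct, because a two-sample t-test on change would fix the pairing and leave the baseline unadjusted.

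Finally, a linear model does not suit every endpoint. The bitter threshold in section 4.4.1 comes from a stepped concentration series. Section 4.4.1 also collects ratings of caffeine alone and of caffeine with HED, so the covariate must be named. An adjusted absolute difference does not by itself answer the plan's criterion of a reduction of more than 30%. These points limit the repair but do not remove the case for it.

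**Conclusion.** The concern holds as a recommendation. A baseline rating exists for every randomised patient, precedes allocation, and is not adjusted for in any planned between-arm analysis. A two-sample t-test on change would be valid, but it would carry −(1−ρ) times any chance baseline difference into the estimate (equal SDs) and would usually be less precise than ANCOVA.

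Under the equal-SD assumptions in the table, the power gain is about 8 points at ρ = 0.3, 6 at 0.5, 3 at 0.7 and 2 at 0.8. It is nil near 0.9 and turns into a loss of about 1 point at 0.95. With unequal SDs it can be smaller or slightly negative. If the plan's 30% and 10% are taken literally, the benefit is precision and protection from chance imbalance only. The documents do not show which of these cases applies. The recommendation rests on the low cost and on the likelihood that a single rating repeated after two weeks correlates well below 0.9, which is a judgement and not a figure from the plan.

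**What to change.** In the Sample Size and Statistical Analysis sections, define the primary analysis as a linear model of the week-3 rating of 500 ppm caffeine alone (without HED) on treatment arm, with the week-1 rating of the same solution as covariate. Report the adjusted HED-minus-placebo difference with its confidence interval and p-value, tested at the stated 1% level. State whether that level is two-sided, and how the criterion of a reduction of more than 30% relates to this result. Keep the between-arm t-test or Mann-Whitney U on changes as a sensitivity analysis.

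Use the same form of model for the between-arm week 1 to week 12 metric endpoints that have a Visit 1 value: caffeine rating, food intake and quality of life. It can also be used for weight and body composition, but little gain is expected there if their correlation over time is high. Leave the stepped bitter threshold to a rank-based or suitably transformed analysis.

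The cost is a few sentences before unblinding, in the same amendment that replaces the paired test. No new data, visits or patients are needed. The statistical price is one degree of freedom (23 instead of 24 with 26 evaluable patients) and the slope-estimation cost of about 1/22 in variance, so precision is slightly lower if ρ exceeds about 0.9.

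### No paired rank test is named for the three within-arm RCT secondary endpoints (or the pilot comparison, if tested); using the named unpaired tests there could miss real within-patient changes

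*Combined protocol and SAP*

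**What the plan says.** Section B.3 (Statistical Analysis) assigns a paired test to one endpoint only: "The primary endpoint will be evaluated using a paired t-test". For all other metric variables the rule is "Metric variables are compared using Student's t-test or the Mann-Whitney U test, depending on normal distribution". No signed-rank or other paired rank test appears anywhere in the document.

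Section 3.3 (Study Endpoints) lists three RCT secondary endpoints that compare two visits of the same women:

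- "Comparison of food intake using a 24-hour recall from week 1 to week 12 within the two groups"
- "Comparison of quality of life using the EORTC-QLQ-30 Ovar and OV-28 from week 1 to week 12 within the two groups"
- patient-related outcomes, compared "using a diary from week 1 to week 12 within the two groups"

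The pilot endpoint has the same structure: "Comparison of taste tests before and during chemotherapy". Section B.1 (Sample Size), however, describes the pilot's purpose this way: "This study is intended to provide a descriptive analysis of taste changes during chemotherapy".

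**The concern.** The question in a within-arm comparison is whether a patient changes between two visits. The Mann-Whitney U test and the unpaired t-test derive their null distributions as if the two sets of values came from different, unrelated patients. Applied to two visits of the same women, they count the stable differences between women as error, which a paired test removes.

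An analyst who follows B.3 and judges one of these variables non-normal finds only one named test, and it does not fit the design. If the variable is judged normal, the text leaves open which form of the t-test to use. At stake is power for three secondary endpoints in arms of 16 or fewer, where power is already limited. The error is conservative: it produces p-values that are too large, and no false claims of change.

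**Working it through.** **Inputs from the documents.** 16 patients per arm and 20% dropout (B.1), so 16 × 0.8 = 12.8, taken as 13. Pilot size is 40 (B.1). The documents give no effect size, visit-to-visit correlation or significance level for these endpoints, and no power figure to reproduce; the calculation behind 32 patients concerns the primary endpoint only.

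**Assumptions.** Two-sided 5%; equal SD σ at both visits; change d in SD units; correlation r between visits, varied from 0 to 0.7.

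**Why pairing matters.** With n patients seen twice, the mean change has variance 2σ²(1 − r)/n. The unpaired test uses 2σ²/n. Its standard error is therefore too large by a factor 1/√(1 − r): 1.20 at r = 0.3, 1.41 at r = 0.5 and 1.83 at r = 0.7.

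**Under no change.** In large samples the unpaired test rejects with probability 2Φ(−1.96/√(1 − r)). This is 5% at r = 0, 1.9% at 0.3, 0.6% at 0.5 and 0.03% at 0.7. Simulation with n = 13 gave 5.0%, 2.5%, 0.9% and 0.2% for Mann-Whitney U. The signed-rank test stayed between 4.1% and 5.2%.

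**Under a change of d = 0.8, n = 13.** The unpaired statistic is centred near d√(n/2) = 0.8 × √6.5 = 2.04 whatever r is. The paired statistic is centred near 2.04/√(1 − r): 2.44 at r = 0.3, 2.88 at 0.5 and 3.72 at 0.7. So unpaired power should stay roughly flat while paired power rises with r. Simulated power (4,000 normal data sets per cell):

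| r | Mann-Whitney U | Signed-rank | Unpaired t | Paired t |
|---|---|---|---|---|
| 0 | 0.446 | 0.436 | 0.487 | 0.458 |
| 0.3 | 0.444 | 0.573 | 0.490 | 0.605 |
| 0.5 | 0.447 | 0.721 | 0.498 | 0.748 |
| 0.7 | 0.449 | 0.918 | 0.505 | 0.929 |

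A separate simulation gave, for Mann-Whitney against signed-rank, about 0.46 and 0.57 (r = 0.3), 0.47 and 0.73 (r = 0.5), and 0.45 and 0.91 (r = 0.7). The two sets agree to within about 0.02. The loss is thus 11 to 13 points at r = 0.3, 26 to 27 at 0.5, and 46 to 47 at 0.7.

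**Sensitivity.**

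- All 16 patients retained, d = 0.5: Mann-Whitney 0.213, 0.198 and 0.165 against signed-rank 0.334, 0.454 and 0.661 (r = 0.3, 0.5, 0.7).
- Skewed (log-normal) data, n = 16, shift of 0.5 SD on the log scale: 0.201 against 0.410 at r = 0.5, and 0.167 against 0.620 at r = 0.7. At r = 0 it is 0.248 against 0.242. The loss is therefore not an artefact of normal data.
- Pilot, n = 40, if tested: at d = 0.5 and r = 0.5, 0.593 against 0.846. At d = 0.8, Mann-Whitney has at least 0.926 at every correlation tried.

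**The case against.** The strongest reply is that B.3 never assigns Mann-Whitney U to the within-arm endpoints. The sentence sits among remarks on descriptive presentation and group comparisons, and Student's t-test does not exclude the paired form. On that reading the within-patient test is unspecified rather than wrong. This stands in part, and it is why the point is conditional. But the rule is the only one given for non-primary metric variables, and it leaves no valid rank test for paired data. On either reading the same sentence is needed.

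Four stronger readings are tempting, and the documents do not support them:

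- **Real changes would be missed.** They could be. The loss depends on a correlation the documents do not give, is nil at zero, and applies only if an unpaired test is actually used.
- **The pilot will fail to show taste changes.** B.1 calls its analysis descriptive, so a formal test is not clearly planned.
- **Non-normality is near certain because thresholds are stepped and bitterness is scored 0 to 10.** Those variables are not among the three within-arm RCT endpoints. Whether food intake, quality of life and diary scores will be judged non-normal cannot be known from the text.
- **The categorical rule has the same fault.** B.3 says "Categorical variables are compared using the chi-square test", but section 3.3 names no yes/no endpoint compared within patients.

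It is also fair to say that within-arm changes do not establish efficacy. Food intake and quality of life have between-arm counterparts in section 3.3 for which the named tests are suitable. Only the diary outcomes have none. That limits the consequence but does not remove the gap.

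**Conclusion.** The point holds as a gap in B.3 with a conditional cost. Three RCT secondary endpoints, and the pilot comparison if it is tested, are paired, and the plan names no paired rank test and does not state the form of the t-test for them.

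The size depends on the assumed correlation: in an arm of 13 with a 0.8 SD change, the power loss is modest at 0.3 and substantial from 0.5 upward. The change, the correlation and the two-sided 5% level are all assumptions. The fault should be corrected, but it does not threaten the trial's main conclusion, because the primary endpoint and the between-arm comparisons do not depend on it.

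**What to change.** In B.3:

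1. Limit the unpaired Student's t-test and the Mann-Whitney U test to comparisons between the two arms.
2. For comparisons of two visits in the same patients, name the paired t-test on the within-patient change, or the Wilcoxon signed-rank test if the changes are not normal. Normality should be judged on the changes, not on the values at each visit.
3. Report the mean or median within-patient change with its 95% confidence interval. For the descriptive pilot, report that change and interval.

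The cost is one or two sentences. No patients, visits or data are added, and these are standard procedures in the software the plan names.

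### The predictive-factor analysis needs an undefined yes/no response for a seven-variable logistic model, although the bitterness rating is declared continuous; a linear model of the rating would be better

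*Combined protocol and SAP*

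**What the plan says.** Section B.1 (Sample Size) describes the outcome: "The patient rates bitterness perception on a continuous scale from 0 to 10". It concludes: "The study endpoint is therefore a continuous variable". For the sample size it assumes a mean reduction of 30% under HED with a standard deviation of 10%.

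Section B.3 (Statistical Analysis) adds a further analysis: "The study will investigate predictive factors for response to the intervention". The method follows: "These analyses are performed using a multivariate binary logistic regression model". Seven variables enter: age, number of chemotherapy cycles, BMI, bowel resection, polyneuropathy, nausea and diarrhoea.

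B.3 does not say what counts as response in an individual patient, at which visit, or whether one or both arms enter. The only threshold in the plan is in its definition of efficacy, "a reduction in the perception of bitterness by more than 30% in the treatment group compared to the placebo group", which contrasts two groups and is not a rule for classifying one patient. The analysis is not among the endpoints in section 3.3, and no significance level or power is stated for it.

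**The concern.** Binary logistic regression needs a two-valued outcome. Section 4.1.5 says efficacy is judged by the caffeine bitterness rating, so the natural reading is that the rating, or its change, will be cut into responders and non-responders. No reason for a cut is given.

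Three consequences follow. Differences in rating on the same side of the cut are thrown away. If the cut were 30%, it would sit at the assumed HED mean, where patients are densest, so reductions of 29% and 31% would count as opposite while 31% and 60% would count as the same. And because no cut is fixed, it could be chosen after the data are seen. A linear model of the rating needs no cut.

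At stake is whether this analysis can give usable estimates. Section C.1.1 says the data are meant to help plan a larger study.

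**Working it through.** The plan gives no power figure for this analysis, so there is none to reproduce. Its sample size of 32 belongs to the primary endpoint.

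**Inputs from the plan.** 32 patients, 16 per arm; 20% dropout, so 16 × 0.8 = 12.8, about 13 per arm; mean reduction 30%, SD 10%; seven variables.

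**Inputs assumed.** HED arm only; response means a reduction above 30%; two-sided 5%; factor-change correlation r of 0.3, 0.5 or 0.7.

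**Step 1: one continuous factor.** Simulate change = 30 + 10·(r·x + √(1 − r²)·e), with x and e standard normal, 1,500 runs per setting. Test x by linear regression on the change, and by logistic regression on the indicator of change > 30.

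| n | r | Linear | Logistic, likelihood ratio | Logistic, Wald | Linear minus likelihood ratio |
|---|---|---|---|---|---|
| 16 | 0.3 | 19.6% | 16.9% | – | 2.7 points |
| 16 | 0.5 | 52.9% | 42.6% | 9.7% | 10.3 points |
| 16 | 0.7 | 89.2% | 74.4% | 18.1% | 14.8 points |
| 13 | 0.3 | 17.7% | 16.1% | – | 1.6 points |
| 13 | 0.5 | 43.9% | 34.9% | 0.5% | 9.0 points |
| 13 | 0.7 | 80.9% | 67.1% | 1.9% | 13.8 points |

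Independent repeats agree within simulation error. Across them the loss is about 0 to 3 points at r = 0.3 and about 6 to 17 points at r = 0.5 to 0.7. With no true effect the likelihood-ratio test rejects in 7 to 8% of runs, so these differences somewhat flatter the logistic model.

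**Step 2: other assumptions.** Take a factor present in half the patients, a difference of d standard deviations between its levels, and n patients per level.

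- Continuous outcome: power = Φ(d·√(n/2) − 1.96). With n = 16 and d = 0.5 this is Φ(1.414 − 1.96) = 29.3%.
- Outcome cut at the median: p₁ = Φ(0.25) = 0.599 and p₂ = 0.401. Power = Φ[(0.197 − 1.96·√(2·0.25/16)) / √(2·0.599·0.401/16)] = 19.5%.
- Loss: 29.3 − 19.5 = 9.8 points.

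With the median cut, for d from 0.5 to 0.8, the loss runs from 4.3 to 11.4 points with 13 patients in total and from 9.8 to 20.3 points with 32. With 30% responders and 32 patients it is 11.4 to 24.7 points. The overall range is about 4 to 25 points.

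**Step 3: the seven variables as planned.** The smaller outcome class holds at most 8 patients in one arm of 16 (8/7 = 1.1 per variable), or at most 16 if all 32 enter (16/7 = 2.3 per variable). Simulating one arm of 13 to 16 patients:

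- complete separation in about 30 to 84% of runs, depending on the inputs assumed;
- Wald power near 0%;
- likelihood-ratio type I error about 21 to 26% at a nominal 5%;
- linear model: type I error 5%, power about 19 to 32% at r = 0.5.

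If all 32 patients enter, likelihood-ratio type I error is still about 12 to 13%.

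**The case against.** **No cut is documented.** B.3 names no response variable, so the cut at 30% is an inference. This stands. A reader might infer that the plan classifies each patient by a reduction of more than 30%, but that threshold is a group contrast. What survives is that some yes/no outcome is required and that the plan calls its own measure continuous.

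**The power loss is not a property of the plan.** Correlation, cut, significance level and the single factor are all assumed, and for a weak factor the loss almost vanishes. This also stands, so no single loss figure should be quoted. The direction is consistent across the settings examined; the size is not.

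**A linear model does not rescue seven variables.** With the week-1 score added there are eight covariates, leaving 16 − 9 = 7 or 13 − 9 = 4 residual degrees of freedom. At r = 0.5, power is then about 29% and 19%, well below the 53% and 44% of the one-factor case. This stands and shapes the fix.

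**Two stronger readings fail.** One is that the placebo arm would contain almost no responders: P(Z > 30/10) = 0.1%. This assumes no change at all under placebo, whereas section C.1.1 allows for a partial placebo reduction. The other is that separation is a problem even with one factor. In that setting it is uncommon; it becomes frequent only with the seven-variable model.

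**The analysis is peripheral.** It is not a listed endpoint and carries no error-rate claim. This is correct and limits the severity.

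**Conclusion.** The point holds in a limited form. The plan pairs an outcome it calls continuous with a binary logistic model, gives no reason, and does not define response for a patient. Modelling the rating on its own scale is the better and cheaper method.

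The information lost by cutting ranges from negligible for a weak factor to about 6 to 17 points of power for a moderate or strong one in a single arm, and about 4 to 25 points under other assumptions. All of these rest on assumed factor strengths and cuts. The firmer ground is the planned model itself: with seven variables and 13 to 16 patients, the logistic fit often separates and neither of its usual tests can be relied on, while the linear model at least keeps its nominal error rate.

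It would go too far to say that the binary model will miss every real factor, or that the linear model makes the analysis well powered. The primary comparison is unaffected and severity is low.

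**What to change.** In B.3, replace the binary logistic model with a linear model of the week-3 bitterness score for 500 ppm caffeine, with the week-1 score as covariate. Then:

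- state which arms enter; if both do, include treatment and a factor-by-treatment term, since without them the model would not identify predictors of response to HED;
- examine the factors one at a time, or in a reduced set named in advance;
- report effects in scale points with 95% confidence intervals;
- label the analysis exploratory;
- if a responder proportion is wanted, give it descriptively with its patient-level definition.

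This costs a few sentences in B.3 and no new data. The downsides are that effects are no longer expressed as odds ratios, and that power remains limited at this sample size.
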